2 SYNOPSIS

Name of Sponsor/Company: Alzamend Neuro, Inc.	Individual Study Table Referring to Part of the Dossier	(For National Authority Use Only)
Name of Finished Product: AL001	Volume:	
Name of Active Ingredient: Lithium salicylate/L-proline cocrystal	Page:	
Title of Study: A Multiple-Dose, Steady-State, Double-Blind, Ascending Dose Safety, Tolerability, Pharmacokinetic Study of AL001 in Patients with Mild to Moderate Alzheimer's Disease and Healthy Adult Subjects ("MAD Study")		
Principal Investigators: Site 001 (Alzheimer's Subjects [Phase 2a]): [name], Clinical Principal Investigator CenExel iResearch, LLC Site 002 (Healthy Subjects [Phase 1]): [name], Clinical Principal Investigator Altasciences Company, Inc.		
Study Centers: Site 001 (Alzheimer's Subjects [Phase 2a]): CenExel iResearch, LLC [name] United States of America (USA) and [name] USA Site 002 (Healthy Subjects [Phase 1]): Altasciences Company Inc. [name]		
Publication (reference): None at the time of this report		
Study Period: Study Initiation Date: 2022/05/04 Study Completion Date: 2023/05/15	Phase of Development: Phase 1 (Healthy Subjects [Canada]) Phase 2a (Alzheimer's Subjects [USA])	

Name of Sponsor/Company: Alzamend Neuro, Inc.	Individual Study Table Referring to Part of the Dossier	(For National Authority Use Only)
Name of Finished Product: AL001	Volume:	
Name of Active Ingredient: Lithium salicylate/L-proline cocrystal	Page:	
Objectives:		
Primary		

To evaluate the safety and tolerability of AL001 under multiple-dose, steady-state conditions in Alzheimer's disease (AD) subjects and healthy adult subjects.		
Secondary		

To characterize the maximum tolerated dose (MTD) of AL001 in subjects with mild-to-moderate AD and healthy adult subjects.		
Exploratory		

To explore the difference in pharmacokinetic (PK) profile between the non-elderly vs elderly subjects (healthy subjects only).For AD subject cohorts (Cohorts 1, 2b, 3b, 4b, and 5b), determination of qualitative and quantitative evaluations of AD subject desirable characteristics for future Phase 2 and 3 clinical studies in order to:
facilitate recruitment into subsequent AL001 clinical trials.facilitate trial-adherence to completion of study requirements including treatment adherence.		
Study Design and Conduct:		
This was a Phase 1/2a, multi-center, double-blind, placebo-controlled, randomized, multiple ascending dose (MAD) clinical study to determine the safety and maximum tolerated dose (MTD) of AL001 in subjects with mild-to-moderate AD (Food and Drug Administration Classification of Stage 2 to 4 AD) and healthy adult subjects. Cohorts 1, 2b, 3b, 4b, and 5b were planned to include AD subjects (between the ages of 50 and 80 years, inclusive) and Cohorts 2a, 3a, 4a, and 5a were planned to include healthy subjects (non-elderly adults between the ages of 18 to 64 years, inclusive, and healthy elderly adults between the ages of 65 to 80 years, inclusive).		
Each cohort was enrolled sequentially and randomized separately using a standard computerized method. The data from the previous cohort was deemed safe before the next sequential cohort was enrolled and dosing initiated.		
Cohort 1 was planned to include 8 AD subjects (6 active and 2 placebo). Each of the Cohorts 2 to 5 was sub-divided into 2 cohorts: Cohorts 2a, 3a, 4a, and 5a (healthy subjects) and Cohorts 2b, 3b, 4b, and 5b (AD subjects).		
At each dose level in Cohorts 2 to 5, the healthy subject cohort "a" (up to 8 subjects) was first completed up to Day 15 and the blinded safety (laboratory reports, AEs, tolerability) and PK data collected up to that point were reviewed by the Safety Review Committee. The initiation of the next dose cohort could be delayed up to approximately 4 weeks following the last dose of the last subject in the preceding cohort to allow for this process. If the dose level was endorsed as safe, the committee permitted progression to the AD subject cohort "b" at the same dose level, as well as progression to the next dose level of healthy subject cohort. The healthy subject cohorts proceeded to the next higher dose level		

Name of Sponsor/Company: Alzamend Neuro, Inc.	Individual Study Table Referring to Part of the Dossier	(For National Authority Use Only)
Name of Finished Product: AL001	Volume:	
Name of Active Ingredient: Lithium salicylate/L-proline cocrystal	Page:	

without having to wait for the corresponding AD subject cohort to be completed and reviewed by the Safety Review Committee.

Cohort 5b was planned but was not conducted due to PK-based stopping rules designed to assure that the assigned MTD is unlikely to result in plasma trough lithium concentrations above 1.0 mEq/L (healthy elderly and Alzheimer's subjects) and 1.2 mEq/L (healthy non-elderly subjects). For salicylate, the maximum threshold value was 30 mg/dL for all subjects. These values pertain to subjects/patients with adequate renal function (estimated glomerular filtration rate [eGFR] \geq 60 mL/minute/1.73 m²).

For each cohort in which the subjects were dosed, subjects were randomized to 1 of 2 treatment groups in a 6:2 ratio of AL001 (active study medication) to placebo. Subjects in each of these cohorts were dosed 3 times daily (TID) for 14 days at the planned dose level indicated in the table below or placebo:

Cohort	Lithium Carbonate Equivalent Daily Dosing Level	No. of AL001 210 mg Capsules	AL001 Daily Dose
Cohort 1	60% of 450 mg lithium carbonate	3 capsules TID	1890 mg \times 14 days
Cohort 2a/ Cohort 2b	100% of 450 mg lithium carbonate	5 capsules TID	3150 mg \times 14 days
Cohort 3a/ Cohort 3b	140% of 450 mg lithium carbonate	7 capsules TID	4410 mg \times 14 days
Cohort 4a/ Cohort 4b	160% of 450 mg lithium carbonate	8 capsules TID	5040 mg \times 14 days
Cohort 5a/ Cohort 5b	200% of 450 mg lithium carbonate	10 capsules TID	6300 mg \times 14 days ^a

Abbreviation: TID = 3 times daily.

Note: 7 mg of AL001 has the lithium content of 1 mg lithium carbonate

a. Lithium dose equivalent to that routinely used for bipolar disorder type 1 treatment.

Subject population:

Cohorts 1, 2b, 3b, 4b, and 5b:

Male and female adult subjects with mild-to-moderate AD, between the ages of 50 and 80 years, inclusive

Cohorts 2a, 3a, 4a, and 5a:

Healthy adult male and female subjects, between the ages of 18 to 64 years, inclusive (non-elderly) and between the ages 65 to 80 years, inclusive (elderly).

Name of Sponsor/Company: Alzamend Neuro, Inc.	Individual Study Table Referring to Part of the Dossier	(For National Authority Use Only)
Name of Finished Product: AL001	Volume:	
Name of Active Ingredient: Lithium salicylate/L-proline cocrystal	Page:	
Number of subjects (planned and analyzed):		
Planned for inclusion: 
• 40 AD subjects (5 cohorts of 8 subjects each)• 32 healthy subjects (4 cohorts of 8 subjects each)		
Included: 
• 33 subjects in AD cohorts• 32 subjects in healthy cohorts		
Participation discontinued: 
• 1 subject in AD cohorts• 2 subjects in healthy cohorts		
Included in the Safety Analysis Set: 
• 33 subjects in AD cohorts• 32 subjects in healthy cohorts		
Included in the PK Analysis Set: 
• 25 subjects in AD cohorts• 24 subjects in healthy cohorts		
Investigational product: Name: AL001 210 mg Immediate Release Capsules Dosage form/Route of administration: Capsule/Oral Regimen: TID dose administrations (8 AM, 2 PM, and 8 PM) for 14 days Batch number: B210312		
Placebo: Description: Placebo for AL001 210 mg Immediate Release Capsules Dosage form/Route of administration: Capsule/Oral Regimen: TID dose administrations (8 AM, 2 PM, and 8 PM) for 14 days Batch number: B220065		

Name of Sponsor/Company: Alzamend Neuro, Inc.	Individual Study Table Referring to Part of the Dossier	(For National Authority Use Only)
Name of Finished Product: AL001	Volume:	
Name of Active Ingredient: Lithium salicylate/L-proline cocrystal	Page:	

Study Duration and Subject Confinement:

The study consisted of 3 phases:

1. Screening Phase – up to 28 days (from Days -28 to -1)
2. Treatment Phase – 16 days (from Day -1 to Day 15):
 - Subjects were admitted to the study site on Day -1. Subjects received 14 days of TID dosing with assigned study medication from Days 1 to 14 and remained confined until Day 15.
3. Follow-up Phase - 1 month
 - Subjects were followed up after discharge from the study site on Day 15, with a post-treatment clinic visit on Day 23 and a post-treatment telephone call on Day 42.

Each subject participated in the study for up to approximately 2.5 months.

Criteria for Evaluation/Endpoints:

Pharmacokinetics:

- Prevalence of peak salicylate plasma concentrations above 30 mg/dL
- Prevalence of trough plasma lithium concentrations above 1.2 mEq/L for healthy adult subjects or 1.0 mEq/L for healthy elderly and AD subjects.

Descriptive statistics for PK were represented by treatment group and compared between non-elderly and elderly subjects.

Safety:

Safety assessments included vital signs (blood pressure, heart rate, and oral body temperature), 12-lead electrocardiogram (ECG), physical examination, safety laboratory tests (hematology, chemistry [including thyroid stimulating hormone, vitamin B12, and magnesium], hemoglobin A1c (HbA1c), and urinalysis, and reported and observed AEs/serious AEs (SAEs)/tolerability observations including signs and/or symptoms of lithium and/or salicylate toxicity.

Demographic characteristics of all screened and successfully enrolled AD subjects were documented.

Statistical methods:

Pharmacokinetics:

In order to characterize the MTD of AL001 in subjects with AD and healthy subjects, descriptive statistics are presented by treatment group for each cohort and overall for the following:

- Proportion of healthy non-elderly subjects with trough lithium concentrations >1.2 mEq/L
- Proportion of subjects with peak (C_{max}) salicylate concentrations >30 mg/dL
- Proportion of healthy elderly and, separately, AD subjects with plasma trough measurements of lithium >1.0 mEq/L

Name of Sponsor/Company: Alzamend Neuro, Inc.	Individual Study Table Referring to Part of the Dossier	(For National Authority Use Only)
Name of Finished Product: AL001	Volume:	
Name of Active Ingredient: Lithium salicylate/L-proline cocrystal	Page:	

Summary statistics of the plasma concentration data were calculated for the PK population, unless otherwise indicated. Summary statistics were calculated for concentration at each individual time point.
 
Concentration data were summarized by treatment group and compared between non-elderly and elderly subjects only for healthy cohorts using the following statistics: number of observations (N), arithmetic mean (mean), SD, geometric mean, minimum (min), median, maximum (max), and coefficient of variation (CV).
 
For healthy subject cohorts, to explore differences in PK between non-elderly and elderly subjects, descriptive statistics were presented by treatment group.
		

Safety Statistical Methodology:
 
Descriptive statistics were used to summarize AEs, safety results and demographic variables (age, height, weight, and body mass index).
		

Summary - Conclusions
 
Pharmacokinetic Results:
 
The observed AL001 MTD (the Cohort 4a/4b dosing level, 1680 mg given TID at 8 AM, 2 PM, and 8 PM, total daily dose 5040 mg) provided lithium at a lithium carbonate equivalent dose of 240 mg TID (720 mg daily) or a lithium citrate oral solution or syrup (8 mEq/5 mL) equivalent dose of 4 mL TID (19.2 mEq daily), all under fasted conditions. With respect to salicylate, these levels of exposure can be justified as safe a posteriori since they are less than the maximum for prescriptive aspirin/salicylate indications and are to be used for a serious medical condition. There were no undue safety concerns identified in the AL001-ALZ02 Study and so none were considered to be related to PK exposures. The MTD was selected to mitigate or obviate the need for AL001 therapeutic drug monitoring (TDM) in targeted neurodegenerative, neurological, and neuropsychiatric conditions, at least for subjects without undue renal compromise.
 
Under the conditions of this study, no clinically obvious or relevant lithium or salicylate PK differences were observed between non-elderly and elderly healthy subjects.
 
There were no obvious demographic characteristics observed under the conditions of this study that can be used to improve future enrollments when screening subjects.
		

Safety Results:

AD Subject Cohorts

- No deaths or SAEs occurred during the study. No subject prematurely discontinued the study due to a treatment-emergent AE (TEAE).
- AL001 was well tolerated in AD subjects regardless of their comorbidities and concomitant medications.
- A total of 24 TEAEs were experienced by 12 of 25 subjects who received AL001 and 6 TEAEs were experienced by 4 of 8 subjects in the pooled placebo group. The proportion of AD subjects with TEAEs increased with increasing dose levels of AL001, with the lowest proportions of subjects in Cohorts 1 (14.3%; AL001 1890 mg) and 2b (16.7%; AL001 3150 mg), and the highest proportion observed (83.3%) in Cohorts 3b (AL001 4410 mg) and 4b (AL001 5040 mg). The proportion of subjects with TEAEs in the pooled placebo group (50.0%) was between that observed in AL001 Cohorts 2b and 3b.
- All TEAEs were experienced by only 1 subject who received either AL001 or placebo, except headache (1 of 6 subjects [16.7%] each in Cohorts 3b and 4b) and pollakiuria (2 of 6 subjects [33.3%] in Cohort 4b).
- No AEs of special interest were reported for AD subjects.

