Name of Sponsor/Company: Alzamend Neuro, Inc.	Individual Study Table Referring to Part of the Dossier	(For National Authority Use Only)
Name of Finished Product: AL001	Volume:	
Name of Active Ingredient: Lithium salicylate/L-proline cocrystal	Page:	
Conclusion: 
Under the conditions of this study, multiple dose administrations of AL001 was well tolerated in healthy elderly and non-elderly subjects, and in subjects with AD, regardless of their comorbidities and concomitant medications.The observed AL001 MTD (1680 mg given TID at 8 AM, 2 PM, and 8 PM, total daily dose 5040 mg) provided lithium at a lithium carbonate equivalent dose of 240 mg TID (720 mg daily) or a lithium citrate oral solution or syrup (8 mEq/5 mL) equivalent dose of 4 mL TID (19.2 mEq daily), all under fasted conditions. The MTD was selected to mitigate or obviate the need for TDM in targeted neurodegenerative, neurological, and neuropsychiatric conditions, at least for subjects without undue renal compromise.With respect to salicylate, these levels of exposure can be justified as safe a posteriori since they are less than the maximum for prescriptive aspirin/salicylate indications and are to be used for a serious medical condition.No clinically obvious or relevant lithium or salicylate PK differences were observed between non-elderly and elderly healthy subjects, under the conditions of this study.No obvious demographic characteristics were observed under the conditions of this study that can be used to improve successful future enrollments when screening subjects.		
Date of Report: 2024/10/30

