6 DEMOGRAPHIC AND OTHER BASELINE CHARACTERISTICS

Unless otherwise specified, all available data will be listed, summarized, for demographics and other baseline characteristics, and presented for all study population as detailed in Table 4. The screened analysis set will be used for exploratory analysis.

Table 4: Data Presentations for Demographic and Other Baseline Characteristics

Data	Variables	Presentation
Demographic and Other Baseline Characteristics	Sex, age, ethnicity, race, height, weight and body mass index (BMI), Mini-Mental State Examination (MMSE) scores, and AD stage FDA classification for AD subjects only	Listing Table – presented for all study populations (Screened, Randomized, Safety and PK).
Medical history	All medical history findings	Listing
Prior and Concomitant medications	All medications taken prior to study drug administration and concomitant medications	Listing

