8 SAFETY ANALYSIS

Unless otherwise specified, all available data will be listed and summary tables for safety assessments will be presented by treatment (dose level of AL001 and pooled placebo) per cohort for the safety population as detailed in Table 5 and all applicable safety data will be presented by combined active and pooled placebo groups, such as, disposition, demographic, adverse events, labs, vital signs, and 12-ECG data.

Continuous variables will be summarized (absolute values and change from baseline) using descriptive statistics (n, mean, SD, minimum, median and maximum).

Table 5: Data Presentations for Safety Assessments

Data	Variables	Presentation
Adverse events	Adverse event (AE) description, date and time (start and end), intensity, relationship to study drug, action taken, study days and outcome	Listing Table
Extent of exposure	Study drug administration dose, units, date, time, cohort	Listing
Clinical laboratory evaluations	Laboratory results (refer to section 8.3 for parameters)	Listing Table
Vital signs	Blood pressure, pulse, and body temperature	Listing Table
Physical examinations	Physical examinations findings	Listing
12-Lead ECGs	ECG interpretations and findings	Listing Table

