8.1 Adverse Events

Treatment-emergent adverse events (TEAEs) are AEs that are not present prior to the exposure to study treatment. All AEs reported following exposure to study treatment are considered TEAEs. All TEAEs will be coded using the Medical Dictionary for Regulatory Activities (MedDRA) Version 25.0. The listing and summaries will include coded System Organ Class (SOC) and Preferred Term (PT).

An overall summary by treatment (dose level of AL001 and pooled placebo and overall) will present the number and percentage of subjects with:

- At least one TEAE
- At least one drug-related TEAE
- Severity intensity

- Mild
- Moderate
- Severe
- Life-threatening
- Death
- at least one SAE
- at least one drug-related SAE
- death

For the study, the following AE tables will also be presented:

- TEAEs by SOC and PT
- SAEs by SOC and PT
- Drug-related TEAEs by SOC and PT
- TEAEs by SOC, PT, and maximum intensity
- TEAEs that lead to premature discontinuation

Events will be listed by treatment, subject and AE onset date. Treatment-emergent AE duration (stop date/time - start date/time) will be included in the listing.

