9.1 Safety Analysis Presentation

Adverse events and medical history will be classified using the MedDRA terminology as defined in the study data management plan (DMP).

Prior and concomitant medications will be coded with the World Health Organization drug dictionary (WHO-DD) (March 2022 B3) as defined in the study DMP.

Generally, summaries will be presented by cohort (dose level of AL001 and pooled placebo, overall). Some summaries will also be presented to include overall (i.e., subject disposition and demographics) Also, applicable safety data will be presented by combined active and pooled placebo groups, such as, disposition, demographic, adverse events, labs, vital signs, and 12-ECG data.

Summaries for data collected at scheduled times specified in the protocol will be presented by cohort (dose level of AL001 and pooled placebo, overall), visit, and, where applicable, time point. Continuous variables will be summarized using the number of observations, mean, standard deviation, minimum, median, and maximum. Categorical variables will be summarized using the number of observations and the corresponding percentage.

In general, the data listings will include data from all subjects who receive at least one dose of either AL001 or placebo.

Study days will be included in adverse event and concomitant medication listings in addition to dates. Study days will be calculated relative to the first day of double-blind treatment (Day 1) derived as (event date - first day of AL001 or placebo dosing) +1 for events after the first day of dosing and (event date - first day of AL001 or placebo dosing) for events before the first day of dosing.

The following general comments also apply to all statistical analyses and data presentations:

- Duration variables will be calculated using the general formula: (end date - start date) +1.
- If the reported value of a clinical laboratory parameter cannot be used in a statistical summary table (e.g., a character string is reported for a parameter of the numerical type), a coded value must be appropriately determined and used in the statistical analyses. In general, a value or lower and upper limit of normal range such as ' <10 ' or ' ≤ 5 ' will be treated as '10' or '5' respectively, and a value such as ' >100 ' will be treated as '100'. However, the actual values as reported in the database will be presented in data listings.

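### The synopsis says AL001 was well tolerated in AD subjects whatever their comorbidities and medications, but the SAP plans no analysis by these factors and the visible text shows only overall counts

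*Protocol*

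**What the plan says.** The claim appears twice in section 2 (Synopsis) of the protocol document. Under Safety Results for the AD cohorts it reads "AL001 was well tolerated in AD subjects regardless of their comorbidities and concomitant medications". The closing Conclusion repeats it in a sentence that also covers healthy subjects: "and in subjects with AD, regardless of their comorbidities and concomitant medications". The closing sentence is limited to the conditions of the study; the Safety Results bullet is not.

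The analysis side is as follows:

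- SAP section 6, Table 4, has a row for "All medical history findings" and a row for "All medications taken prior to study drug administration and concomitant medications". The presentation given for each is a listing. Demographics and baseline characteristics, in the same table, get a listing and a table.
- SAP section 8: "summary tables for safety assessments will be presented by treatment (dose level of AL001 and pooled placebo) per cohort for the safety population". Sections 8.2 to 8.6 and 9.1 use the same kind of breakdown, and one of the two SAP texts in the file adds combined active against pooled placebo.
- SAP section 8.1: "An overall summary by treatment (dose level of AL001 and pooled placebo and overall) will present the number and percentage of subjects with" TEAEs, related TEAEs, SAEs and so on, with no further factor.
- SAP sections 7.1 and 7.2 present PK by treatment and cohort, with an age comparison in healthy subjects only.
- SAP section 9.1: "Prior and concomitant medications will be coded with the World Health Organization drug dictionary (WHO-DD) (March 2022 B3"), so medication classes could be formed, but no tabulation of them is planned.
- The synopsis's own safety methods: "Descriptive statistics were used to summarize AEs, safety results and demographic variables (age, height, weight, and body mass index").

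**The concern.** To say that a drug was well tolerated *regardless of* a factor is to say that tolerability was looked at across levels of that factor and did not change materially. Nothing planned in the SAP would produce that comparison, and nothing visible in the synopsis reports it. The visible text does not even say how many AD subjects had a given comorbidity or took a given class of medication.

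Safety and tolerability in AD and healthy subjects is the primary objective, and this clause sits in its headline conclusion. A reader will take it as a finding about breadth of applicability, when what is shown is that few serious problems occurred overall in a small group.

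**Working it through.** The clause carries no figure of its own, so the check starts from the counts reported beside it.

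**1. Reproduce the TEAE total.** Inputs are the Safety Results for the AD cohorts in the synopsis: 12 of 25 on AL001, 4 of 8 on pooled placebo, and cohort percentages of 14.3% (Cohort 1), 16.7% (2b), 83.3% (3b) and 83.3% (4b). The synopsis gives a denominator of 6 for Cohorts 3b and 4b. Denominators of 7 for Cohort 1 and 6 for Cohort 2b are inferred from the percentages and the total.

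- 1/7 = 14.3%, 1/6 = 16.7%, 5/6 = 83.3%, 5/6 = 83.3%
- Sum: (1 + 1 + 5 + 5)/(7 + 6 + 6 + 6) = 12/25 = 48.0%, exact 95% interval 27.8% to 68.7%
- Placebo: 4/8 = 50.0%, exact 95% interval 15.7% to 84.3%

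The stated figures reproduce.

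**2. What zero events can support.** The AD cohorts had no deaths, SAEs, discontinuations due to a TEAE, or AEs of special interest. Zero overall means zero in every subgroup. The exact two-sided 95% upper limit for 0/n is 1 − 0.025^(1/n):

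| n | Basis | Upper limit |
|---|---|---|
| 25 | all AD subjects on AL001 | 1 − 0.025^(1/25) = 13.7% |
| 12 | assumed subgroup, about half | 1 − 0.025^(1/12) = 26.5% |
| 6 | assumed subgroup, about a quarter | 1 − 0.025^(1/6) = 45.9% |

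The subgroup sizes are assumptions, because the documents give none. In a subgroup of 6, zero observed events are compatible with a true risk of nearly one in two.

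**3. Dose.** The two lower doses gave (1 + 1)/(7 + 6) = 2/13 subjects with a TEAE, and the two higher doses (5 + 5)/(6 + 6) = 10/12. A post hoc Fisher exact test gives p = 0.0012. If a comorbidity or medication happened to be more common in the lower-dose cohorts, pooling over dose would make it look protective; in the higher-dose cohorts, harmful. Any split that respects dose works with six or seven treated subjects per level.

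**4. Could a subgroup table settle it?** Take assumed TEAE risks of 40% and 70% in two subgroups of the 25. The power of a two-sided 0.05 Fisher test is the sum of Bin(a; n1, 0.4) × Bin(b; n2, 0.7) over all tables with p ≤ 0.05. This is 30% for a 13 v 12 split and 14% for 19 v 6. At assumed risks of 30% and 80% it is 72% and 46%. These figures concern differences within the AL001 arm and ignore dose. They illustrate how little 25 subjects can say, and do not estimate a treatment-by-factor interaction.

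**The case against.** The strongest reply is that the sentence can be read modestly: among the AD subjects treated, who brought their own histories and medications, no serious tolerability problem appeared. The study is descriptive, SAP section 3.5 says its size has no statistical basis, and no interaction test is claimed. On that reading the zero counts are direct support, and TEAE incidence was similar on AL001 and placebo (48.0% v 50.0%). The closing Conclusion is also limited to the conditions of the study.

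Much of this stands. A reader might infer that the conclusion has no supporting result at all. The documents do not bear that out, because the zero counts hold in every subgroup and give weak descriptive support.

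A reader might also infer that no one looked at the question. That cannot be known. Only the synopsis of the report is available, part of it between the AD safety results and the Conclusion is missing from the text reviewed, and listings would permit a subject-level review of 25 people. What can be said is that no such analysis was planned and none is visible.

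A third inference, that the clause will set entry criteria for later trials, is not in the documents. The exploratory AD objective on future studies concerns recruitment and adherence, and cites MMSE, FDA stage and demographics.

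The limit to study conditions does not rescue the wording. It restricts the setting but supplies no comparison, and it is absent from the Safety Results bullet. If the modest reading is the one intended, the sentence should say so.

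**Conclusion.** The clause claims more than the planned analyses or the visible results can carry. The overall counts support a statement that no death, SAE, TEAE-related discontinuation or AE of special interest was observed in the AD cohorts. They leave room for a true risk of up to 13.7% in the 25 treated subjects, and up to 26.5% or 45.9% in subgroups of 12 or 6 if such subgroups existed. They do not show that tolerability is independent of comorbidity or medication.

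Nor is there evidence of the opposite: nothing in the documents suggests that tolerability was worse with any comorbidity or medication. No endpoint, analysis set, reported count or dose conclusion changes.

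This is a correction to the wording of a primary-objective conclusion, worth making because it is specific and almost free. It rests on the inferred cohort denominators, the assumed subgroup sizes, and the synopsis text that is available.

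**What to change.** Delete the clause about comorbidities and concomitant medications in both places. Alternatively, replace it with what was observed, for example: 'There were no deaths, SAEs or discontinuations due to a TEAE in the enrolled AD subjects, who had various comorbidities and concomitant medications; tolerability by these factors was not a planned analysis.' The description of the subjects' histories and medications should be confirmed against the listings before it is used.

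If the sponsor already holds a review by these factors, cite it and label it post hoc. If a table is added, it should be optional and descriptive: TEAEs by main comorbidity and medication class, shown by dose level with n/N and 95% intervals, and labelled post hoc. The report is dated 2024/10/30 and shows results by treatment, so the classes can no longer be prespecified. Such a table could inform the reader but could not by itself restore the deleted clause.

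The cost is one edited clause in two places and a slightly less favourable conclusion. The optional table would use data already collected.
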